5.1 Inclusion Criteria

- 1. Admitted to a hospital with symptoms suggestive of COVID-19 and requires ongoing medical care.
- 2. Subject (or legally authorized representative) provides informed consent prior to initiation of any study procedures.
- 3. Subject (or legally authorized representative) understands and agrees to comply with planned study procedures.
- 4. Male or non-pregnant female adult ≥ 18 years of age at time of enrollment.
- Illness of any duration and has laboratory-confirmed SARS-CoV-2 infection as determined by PCR or other commercial or public health assay (e.g., Nucleic Acid Amplification Test [NAAT], antigen test) in any respiratory specimen or saliva ≤14 days prior to randomization.
- 6. Illness of any duration, and requiring, just prior to randomization, supplemental oxygen (any flow), mechanical ventilation or ECMO (ordinal score 5, 6, or 7).
- 7. Women of childbearing potential must agree to either abstinence or use at least one acceptable method of contraception from the time of screening through 5 months post study IP dosing.

Note: Acceptable methods include barrier contraceptives (condoms or diaphragm) with spermicide, intrauterine devices (IUDs), hormonal contraceptives, oral contraceptive pills, and surgical sterilization.

8. Agrees not to participate in another blinded clinical trial (both pharmacologic and other types of interventions) for the treatment of COVID-19 through Day 29 (see Section 5.4 for more information about concurrent trial participation).

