6.3 Measures to Minimize Bias: Randomization and Blinding

Randomization will be a two-step process. Patients will first be randomized to one of the stages to which they are eligible (e.g., risankizumab or other interventions) with equal allocation. Then

patients are randomized to the active or placebo version of that intervention with allocation k:1, where k is the number of eligible stages the study site is currently randomizing. All eligible subjects will receive backbone therapy comprising remdesivir. Patients randomized to risankizumab in the first stage will be randomized to receive either risankizumab/remdesivir or placebo/remdesivir in the second stage. Randomization will be stratified by:

- Site
- Severity of illness at enrollment: baseline Ordinal Score 5 versus Ordinal Score 6 or 7 combined

The randomization procedure will be described in the MOP.

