	Subgroup	Repeat the primary analysis for this endpoint within each of the following subgroups: 
 Actual baseline ordinal score Baseline steroid use Baseline use of emerging COVID-19 treatments Duration of symptoms prior to enrollment (only using the \leq Median; $>$ Median classification)
9. Incidence of new invasive ECMO use through study Day 29 for subjects with baseline clinical status of 5 or 6;	Primary	
 No covariate adjustment
10. Days a subject who has a baseline clinical status of 5 or 6 has a clinical status > 6 up to and including Study Day 29;	Primary	
 No covariate adjustment
	Subgroup	Repeat the primary analysis for this endpoint within each of the following subgroups: 
 Actual baseline ordinal score Baseline steroid use Baseline use of emerging COVID-19 treatment Duration of symptoms prior to enrollment (only using the \leq Median; $>$ Median classification)
11. Proportion of subjects alive and without respiratory failure at Study Day 29;	Primary	
 No covariate adjustment
12. Time (days) to death or ventilation up to and Including Day 29	Primary	Adjust for the following covariates: 
 Baseline dexamethasone use Actual baseline ordinal score Baseline CRP value (Continuous) Age (continuous)

Endpoint	Analysis	Covariates/Subgroups
13. Days of hospitalization from date of admission by Study Day 29.	Primary	
 No covariate adjustment for this analysis
	Subgroup	Repeat the primary analysis for this endpoint within each of the following subgroups: 
 Actual baseline ordinal score Baseline steroid use Baseline use of emerging COVID-19 treatment Duration of symptoms prior to enrollment (only using the <= Median; > Median classification)
Other Secondary Endpoints: Safety		
1. Values of CRP ferritin, D-dimer, LDH, and fibrinogen on Study Day 1: Study Days 3, 5, 8, 11,15 and 29	Primary	
 No covariate adjustment
2. 14-day Mortality	Primary	1. Adjust for the following covariates: 
 Actual baseline ordinal score Baseline steroid use
3. 28-day Mortality	Primary	1. Adjust for the following covariates: 
 Actual baseline ordinal score Baseline steroid use

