11. Proportion of subjects alive and without respiratory failure at Study Day 29;	Primary	
 Use the complete data for ordinal score to define survival without respiratory failure. Subjects will be considered events at Day 29 if they are dead or are on invasive mechanical ventilation/ECMO anytime between Day 26 and Day 32 (Window for Day 29) regardless of their baseline ordinal score. All subjects who died before Day 26 (beginning of Day 29 visit window) will be considered events. All subjects who died after Day 32 or those who were not on invasive mechanical ventilation/ECMO between Day 26 and Day 32 will be considered non-events.
12. Time (days) to ventilation or death up to and including Day 29;	Primary	
 Use the complete data for ordinal score to define survival without respiratory failure. All subjects whose last assessment in the study is before Day 26 and before progression to mechanical ventilation or death will be considered non-events and censored at the date of their last observed assessment. Subjects who complete follow-up without mechanical ventilation or death will be censored at the expected study Day 29. Subjects whose last assessment in the study is before Day 29 but within window for Day 29 (i.e., Day 26, 27, 28) and before experiencing death or progression to mechanical ventilation will be considered non-events regardless of their discharge status at Day 29.
	Primary with Sensitivity Imputation	
 Use the complete data for ordinal score to define survival without respiratory failure. Subjects whose last assessment in the study is before Day 26 and were discharged to a location other than LTAC, hospice care or other hospital, or progressed to mechanical ventilation or death after Day 29 will be considered non-events and censored at Day 29. Subjects whose last assessment in the study is before Day 26 and before progression to mechanical ventilation or death and without being discharged to a location other than LTAC, hospice care or other hospital at their last assessment will be considered non-events and censored at the date of their last observed assessment. Subjects who complete follow-up without mechanical ventilation or death will be censored at the expected study Day 29.

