Ventilator / ECMO days will be defined as the number of days where the ordinal score > 6 up to and including Study Day 29. The total number of days will be the sum of all reported days, regardless of whether the days occur consecutively or in disjoint intervals. For planned gaps between study days, the day of the qualifying Study Day and the days to the next planned Study Day will be included in the total number of days. The Post-Discharge Supplemental Oxygen CRF questions regarding days of ECMO or invasive ventilation will be used for any time period the subject is not hospitalized at the study hospital. See Section 6.5 for the plan for handling subjects who do not have data through Study Day 29 or die prior to Study Day 29.

Duration of Invasive Mechanical Ventilation/ECMO days will be summarized in a table using medians and quartiles by treatment (Table 38). Bee swarm plots of Invasive Mechanical Ventilation/ECMO days, and days hospitalized by treatment will be generated (Figure 21).

The incidence of new Invasive Mechanical Ventilation/ECMO use will be analyzed by treatment (Table 41). The numerator will only include subjects in category 6 or below at enrollment who change to a category 7 or 8. The denominator will include subjects with a baseline ordinal score of 6 or below. The number of subjects reporting new use of Invasive Mechanical Ventilation/ECMO and the incidence rate along with 95% and 80% CIs estimated using the Blaker method will be reported.

Refer to Table 6 for a list of covariates and subgroup analyses for this endpoint. Refer to Table 7 for imputation methods to be applied to this endpoint.

Proportion of Subjects Alive and Without Respiratory Failure at Study Day 29

The proportion of subjects alive and without respiratory failure at Study Day 29 will be defined as the proportion of subjects with an ordinal score < 7 at any time between Day 26 through Day 32 (Visit window for Study Day 29 Visit). The proportion of subjects with respiratory Failure or death at Day 29 will also be provided. These proportions will be presented by treatment along with 95% and 80% Blaker CIs. Treatment differences will be evaluated using a logistic regression and the p-value will be presented (Table 31).

Refer to Table 6 for a list of covariates and subgroup analyses for this endpoint. Refer to Table 7 for imputation methods to be applied to this endpoint.

Time to Mechanical Ventilation or Death up to and Including Day 29

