CI= Confidence Interval. N=Number of subjects in modified intent-to-treat (mITT) population. n= Number of unique subjects that satisfies the row criteria.									
^a The table includes 80% and 95% Blaker confidence intervals and p-value from the logistic regression with treatment group as the only covariate.									
^b For the subgroup analyses, only the values for the “Alive and Without Respiratory Failure” are presented and analyses similar to those in ^a were performed.									

Table 32: Time to Improvement by at Least One Category through Day 60 in the 8-point Ordinal Scale — mITT Population

Analysis/Subgroup	Treatment	Number of Recovered Subjects		Median Time to Recovery			Hazard Ratio			P-value ^c
		n	%	Estimate	80% CI	95% CI	Estimate	80% CI	95% CI	
Initial Model ^a	Treatment A (N=X)	x	x.x	x.x	x.x, x.x	x.x, x.x	x.x	x.x, x.x	x.x, x.x	0.xxx
	Treatment B (N=X)	x	x.x	x.x	x.x, x.x	x.x, x.x				
Subgroup Analyses^b										
Baseline Ordinal Score										
5	Treatment A (N=X)	x	x.x	x.x	x.x, x.x	x.x, x.x	x.x	x.x, x.x	x.x, x.x	0.xxx
	Treatment B (N=X)	x	x.x	x.x	x.x, x.x	x.x, x.x				
6 or 7	Treatment A (N=X)	x	x.x	x.x	x.x, x.x	x.x, x.x	x.x	x.x, x.x	x.x, x.x	0.xxx
	Treatment B (N=X)	x	x.x	x.x	x.x, x.x	x.x, x.x				
Other	Treatment A (N=X)	x	x.x	x.x	x.x, x.x	x.x, x.x	x.x	x.x, x.x	x.x, x.x	0.xxx
	Treatment B (N=X)	x	x.x	x.x	x.x, x.x	x.x, x.x				
Baseline Steroid Use										
Yes	Treatment A (N=X)	x	x.x	x.x	x.x, x.x	x.x, x.x	x.x	x.x, x.x	x.x, x.x	0.xxx
	Treatment B (N=X)	x	x.x	x.x	x.x, x.x	x.x, x.x				
No	Treatment A (N=X)	x	x.x	x.x	x.x, x.x	x.x, x.x	x.x	x.x, x.x	x.x, x.x	0.xxx
	Treatment B (N=X)	x	x.x	x.x	x.x, x.x	x.x, x.x				
Baseline Use of Emerging Covid-19 Treatments										
Yes	Treatment A (N=X)	x	x.x	x.x	x.x, x.x	x.x, x.x	x.x	x.x, x.x	x.x, x.x	0.xxx
	Treatment B (N=X)	x	x.x	x.x	x.x, x.x	x.x, x.x				
No	Treatment A (N=X)	x	x.x	x.x	x.x, x.x	x.x, x.x	x.x	x.x, x.x	x.x, x.x	0.xxx
	Treatment B (N=X)	x	x.x	x.x	x.x, x.x	x.x, x.x				
Duration of Symptoms Prior to Enrollment Group 1										
≤ Median	Treatment A (N=X)	x	x.x	x.x	x.x, x.x	x.x, x.x	x.x	x.x, x.x	x.x, x.x	0.xxx
	Treatment B (N=X)	x	x.x	x.x	x.x, x.x	x.x, x.x				
> Median	Treatment A (N=X)	x	x.x	x.x	x.x, x.x	x.x, x.x	x.x	x.x, x.x	x.x, x.x	0.xxx
	Treatment B (N=X)	x	x.x	x.x	x.x, x.x	x.x, x.x				

Analysis/Subgroup	Treatment	Number of Recovered Subjects		Median Time to Recovery			Hazard Ratio			P-value ^c
		n	%	Estimate	80% CI	95% CI	Estimate	80% CI	95% CI	

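### The Day 29 test of being alive without respiratory failure omits baseline severity, so it is conservative and loses some power, by an amount the documents do not fix

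*SAP*

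**What the plan says.** SAP Section 8.2.2 says of this endpoint: "Treatment differences will be evaluated using a logistic regression and the p-value will be presented". It names no covariates and refers the reader to Table 6. Table 6, other secondary efficacy row 11 ("Proportion of subjects alive and without respiratory failure at Study Day 29") answers "No covariate adjustment". Footnote a to Table 31 in Appendix 1 repeats this: the p-value is the "p-value from the logistic regression with treatment group as the only covariate".

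The analysis covers every baseline score. Table 7, row 11 counts failures "regardless of their baseline ordinal score", and Protocol Section 5.1 admits subjects with scores 5, 6 and 7. Protocol Section 6.3 stratifies randomisation by site and by "Severity of illness at enrollment: baseline Ordinal Score 5 versus Ordinal Score 6 or 7 combined". SAP Section 6.5.2 does not expect any missing baseline scores.

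**The concern.** A subject who enters at score 7 is already in a state that counts as failure if it persists to Day 29, whereas a subject at score 5 has to deteriorate to reach it. Baseline score is therefore likely to be the strongest single predictor. When a binary endpoint has a strong baseline predictor, and that predictor is balanced by design, a treatment-only test carries between-severity variation as noise. The nominal error rate is not used up and power is lost. Any chance difference between arms in the number of ventilated subjects also passes straight into the comparison. The covariate is already collected in everyone and used elsewhere in the same SAP, so the omission gains nothing.

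**Working it through.** **1. The nearest figure in the plan.** No power is stated for this endpoint. The only stated power is SAP Table 5, for the Day 8 ordinal score. Using the SAP's Whitehead formula with N = 200 in total and category probabilities averaged over arms, V = N(1 − Σp̄³)/12 and power = Φ(√V·ln OR − z). At OR 2 this gives 0.769 (alpha 0.05) and 0.921 (alpha 0.20), against 0.765 and 0.913 stated. Table 5 reproduces, but it does not inform the Day 29 endpoint.

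**2. What the SAP does for close relatives.**

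| Analysis | Baseline score in model? | Where |
|---|---|---|
| Ordinal score at Day 29 | Yes, with steroid use | Section 8.2.2 |
| Through-Day-29 version (baseline 5 or 6 only) | Yes, with dexamethasone, CRP, age | Section 6.4.2, Table 6 |
| 14-, 28- and 59-day mortality | Yes, with steroid use | Table 6, safety rows 2-4 |
| Generic logistic code without MI | Yes, with steroid use | Section 6.1 |
| At-Day-29 version (baseline 5, 6, 7) | No | Table 6 row 11, Table 31 |

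The through-Day-29 version, which excludes ventilated subjects, is adjusted. The version that includes them is not.

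**3. Information lost.** With stratum shares w, failure rates p and overall rate p̄ = Σwp, the large-sample loss near the null from ignoring the strata is

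loss = 1 − Σ w·p(1 − p) / [p̄(1 − p̄)].

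The documents supply neither w nor p, so both are assumed. Example: shares 50/30/20% for scores 5/6/7 and failure rates 10/25/50%.
- p̄ = 0.050 + 0.075 + 0.100 = 0.225, and p̄(1 − p̄) = 0.1744.
- Three levels: 0.5(0.09) + 0.3(0.1875) + 0.2(0.25) = 0.1513. Loss = 1 − 0.1513/0.1744 = 13%.
- 5 versus 6/7: the pooled 6/7 rate is 0.175/0.5 = 0.35, and 0.5(0.09) + 0.5(0.2275) = 0.1588. Loss = 9%.

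**4. Range.** A grid of 1,392 combinations was used: score 5 share 35-75%, score 7 share 5-35%, score 6 the remainder (at least 10%); failure 5-15%, 20-35% and 40-70% for scores 5, 6 and 7.
- Three levels: median 15%, central 80% of combinations 6-28%, extremes 2-44%.
- 5 versus 6/7: median 10%, central 80% of combinations 4-21%.

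**5. Power.** Simulation used 100 per arm, all three score counts balanced, true conditional OR 2, two-sided 0.05 and 40,000 replicates, comparing unadjusted with stratified score tests.

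| Shares 5/6/7 | Failure 5/6/7 | Loss, 3 levels | Loss, 5 vs 6/7 | Power: none / 5 vs 6/7 / 3 levels |
|---|---|---|---|---|
| 70/25/5% | 8/20/40% | 6% | 5% | 0.27 / 0.28 / 0.28 |
| 50/30/20% | 10/25/50% | 13% | 9% | 0.36 / 0.40 / 0.41 |
| 40/30/30% | 10/30/65% | 24% | 15% | 0.38 / 0.44 / 0.48 |
| 45/20/35% | 5/30/70% | 38% | 29% | 0.27 / 0.38 / 0.43 |

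With no treatment effect, the unadjusted test rejected in 0.012 to 0.043 of trials at nominal 0.05, and in 0.10 to 0.185 at nominal 0.20. These rates assume exact balance on all three scores; if only 5 versus 6/7 balances, the test is less conservative.

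**6. Imbalance within the combined stratum.** Suppose 80 subjects are in the 6/7 stratum, 40 per arm, with 30 of the 80 at score 7. By the hypergeometric distribution, the chance that the arms differ by 6 or more score-7 subjects is 25%. Take an 18 versus 12 split, 60 score-5 subjects per arm, and failure rates of 8/25/55%. Expected failures are 4.8 + 5.5 + 9.9 = 20.2 and 4.8 + 7.0 + 6.6 = 18.4 per 100. The odds ratio is then (18.4/81.6)/(20.2/79.8) = 0.89 with no treatment effect.

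**The case against.** **Other analyses already account for severity.** The Day 29 ordinal score is adjusted, time to ventilation or death is adjusted and repeated in the whole mITT population (Table 43), and Table 31 has rows within baseline 5 and within 6 or 7. This limits the harm but does not repair this test. The Table 31 subgroup rows are also treatment-only, still pool 6 with 7, and give no combined adjusted result. Table 6 lists no subgroup analysis for this endpoint at all.

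**Row 11 follows a pattern.** Many other secondary rows in Table 6 are unadjusted, including time to death by Day 29. That is true, but most of the unadjusted efficacy rows are descriptive summaries, whereas this one produces a p-value.

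**Stronger readings that the documents do not support.**
- A reader might infer that a specific 15-30% of the information is lost. That would rest wholly on an assumed mix and assumed rates: 52% of the grid falls below 15% with three levels, and 75% does with 5 versus 6/7. Gain and loss are also easily confused: a squared-z ratio of 1.15 to 1.30 in favour of adjustment is a 15-30% gain, which is a loss of 1 − 1/1.15 = 13% to 1 − 1/1.30 = 23%.
- A reader might infer that a reported odds ratio is pulled toward 1. Table 31 reports no odds ratio. A marginal and a conditional odds ratio are in any case different quantities, and their difference is not bias.
- A reader might infer excess false positives. Stratification limits 5 versus 6/7 imbalance, and with balanced strata the test errs on the conservative side.

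**Conclusion.** The point stands as a matter of efficiency and consistency. The overall Table 31 p-value omits a stratification factor that should predict the outcome strongly, and this is at odds with the SAP's treatment of closely related endpoints and with its own generic code. The direction of the loss follows from the design if failure rates differ by baseline score. Its size does not: about 5-30% of the information with three levels, or about 4-21% with the SAP's coding, holds only under the assumed shares and rates above. In the four power scenarios the gain from three-level adjustment at OR 2 ran from about 1 to 16 percentage points.

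The stakes are limited. One p-value classed as other secondary is affected. The rule for declaring a product promising concerns the primary endpoint (SAP Section 5), and this endpoint is not among those listed for the global and Hochberg analyses in Table 9.

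**What to change.** In Table 6 row 11, Section 8.2.2 and Table 31 footnote a, specify a logistic model with treatment, actual baseline ordinal score and baseline steroid use, in line with the generic code in Section 6.1. Scores 5, 6 and 7 as separate levels are preferable, because this also handles 6 versus 7 imbalance. State how any subject with an actual baseline score of 4 is coded, since several table shells allow for such subjects. Keep the raw proportions with their Blaker intervals. At the same time, reconcile the subgroup rows in Table 31 with Table 6, which lists none for this endpoint.

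The cost is one model statement and aligned wording in three places, with no new data. An adjusted odds ratio or a standardised risk difference is optional. It would add columns to Table 31 and, for the risk difference, the 1,000-sample bootstrap already described in Section 6.1.

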14.3 Safety Data

14.3.1 Displays of Adverse Events

Table 46: Overall Summary of Treatment Emergent Adverse Events by Baseline Ordinal Score — Safety Population

Adverse Event Categories	Treatment A (N=X)												Treatment B (N=X)																	
	Baseline Ordinal Score												Baseline Ordinal Score																	
	5			6			7			Any BOS ^a			5			6			7			Any BOS ^a								
	n	%	Events	n	%	Events	n	%	Events	n	%	Events	n	%	Events	n	%	Events	n	%	Events	n	%	Events	n	%	Events			
At least one TEAE	x	x.x	xxx	x	x.x	xxx	x	x.x	xxx	x	x.x	xxx	x	x.x	xxx	x	x.x	xxx	x	x.x	xxx	x	x.x	xxx	x	x.x	xxx	x	x.x	xxx
At least one TEAE grade ≥ 3	x	x.x	xxx	x	x.x	xxx	x	x.x	xxx	x	x.x	xxx	x	x.x	xxx	x	x.x	xxx	x	x.x	xxx	x	x.x	xxx	x	x.x	xxx	x	x.x	xxx
At least one related TEAE	x	x.x	xxx	x	x.x	xxx	x	x.x	xxx	x	x.x	xxx	x	x.x	xxx	x	x.x	xxx	x	x.x	xxx	x	x.x	xxx	x	x.x	xxx	x	x.x	xxx
At least one related TEAE grade ≥ 3	x	x.x	xxx	x	x.x	xxx	x	x.x	xxx	x	x.x	xxx	x	x.x	xxx	x	x.x	xxx	x	x.x	xxx	x	x.x	xxx	x	x.x	xxx	x	x.x	xxx
At least one treatment-emergent SAE	x	x.x	xxx	x	x.x	xxx	x	x.x	xxx	x	x.x	xxx	x	x.x	xxx	x	x.x	xxx	x	x.x	xxx	x	x.x	xxx	x	x.x	xxx	x	x.x	xxx
At least one TEAE leading to early termination of study	x	x.x	xxx	x	x.x	xxx	x	x.x	xxx	x	x.x	xxx	x	x.x	xxx	x	x.x	xxx	x	x.x	xxx	x	x.x	xxx	x	x.x	xxx	x	x.x	xxx
At least one TEAE leading to study drug discontinuation	x	x.x	xxx	x	x.x	xxx	x	x.x	xxx	x	x.x	xxx	x	x.x	xxx	x	x.x	xxx	x	x.x	xxx	x	x.x	xxx	x	x.x	xxx	x	x.x	xxx
Death	x	x.x	xxx	x	x.x	xxx	x	x.x	xxx	x	x.x	xxx	x	x.x	xxx	x	x.x	xxx	x	x.x	xxx	x	x.x	xxx	x	x.x	xxx	x	x.x	xxx

BOS= Baseline Ordinal Score.

TEAE= Treatment-emergent Adverse Event. N=Number of subjects in the Safety population. n= Number of unique subjects that satisfies the row criteria.

^a There were X additional subjects with an Actual Baseline Ordinal Score of 4 that are included in the ‘Any BOS’ summaries.

Table 47: Treatment Emergent Adverse Events by System Organ Class, Preferred Term and Treatment Group — Safety Population

MedDRA Classification		Treatment A (N=X)			Treatment B (N=X)			Risk Difference	
System Organ Class	Preferred Term	n	%	Events	n	%	Events	Estimate	95% CI ^a
Any SOC	Any PT	x	x.x	xxx	x	x.x	xxx	x.x	x.x
SOC 1	Any PT	x	x.x	xxx	x	x.x	xxx	x.x	x.x
	PT 1	x	x.x	xxx	x	x.x	xxx	x.x	x.x
	PT 2	x	x.x	xxx	x	x.x	xxx	x.x	x.x
SOC 2	Any PT	x	x.x	xxx	x	x.x	xxx	x.x	x.x
	PT 1	x	x.x	xxx	x	x.x	xxx	x.x	x.x
	PT 2	x	x.x	xxx	x	x.x	xxx	x.x	x.x

TEAE= Treatment-emergent Adverse Event. n= Number of unique subjects that satisfies the row criteria. N=Number of subjects in the Safety population. n= Number of unique subjects that satisfies the row criteria.
 Denominators are the number of subjects in the Safety population.
 If a subject has multiple occurrences of an adverse event, the subject is counted only once in the preferred term/system organ class category.
 All adverse events were coded using the Medical Dictionary for Regulatory Activities (MedDRA) version 23.0.
^a 95% CI for risk differences calculated using the Miettinen-Nurminen method.

Table 48: Treatment Emergent Adverse Events by System Organ Class, Preferred Term, and Baseline Ordinal Score — Safety Population

MedDRA Classification		Treatment A (N=X)												Treatment B (N=X)																	
		Baseline Ordinal Score												Baseline Ordinal Score																	
		5			6			7			Any BOS ^a			5			6			7			Any BOS ^a								
		n	%	Events	n	%	Events	n	%	Events	n	%	Events	n	%	Events	n	%	Events	n	%	Events	n	%	Events	n	%	Events			
System Organ Class	Preferred Term																														
Any SOC	Any PT	x	x.x	xxx	x	x.x	xxx	x	x.x	xxx	x	x.x	xxx	x	x.x	xxx	x	x.x	xxx	x	x.x	xxx	x	x.x	xxx	x	x.x	xxx	x	x.x	xxx
SOC 1	Any PT	x	x.x	xxx	x	x.x	xxx	x	x.x	xxx	x	x.x	xxx	x	x.x	xxx	x	x.x	xxx	x	x.x	xxx	x	x.x	xxx	x	x.x	xxx	x	x.x	xxx
	PT 1	x	x.x	xxx	x	x.x	xxx	x	x.x	xxx	x	x.x	xxx	x	x.x	xxx	x	x.x	xxx	x	x.x	xxx	x	x.x	xxx	x	x.x	xxx	x	x.x	xxx
	PT 2	x	x.x	xxx	x	x.x	xxx	x	x.x	xxx	x	x.x	xxx	x	x.x	xxx	x	x.x	xxx	x	x.x	xxx	x	x.x	xxx	x	x.x	xxx	x	x.x	xxx
SOC 2	Any PT	x	x.x	xxx	x	x.x	xxx	x	x.x	xxx	x	x.x	xxx	x	x.x	xxx	x	x.x	xxx	x	x.x	xxx	x	x.x	xxx	x	x.x	xxx	x	x.x	xxx
	PT 1	x	x.x	xxx	x	x.x	xxx	x	x.x	xxx	x	x.x	xxx	x	x.x	xxx	x	x.x	xxx	x	x.x	xxx	x	x.x	xxx	x	x.x	xxx	x	x.x	xxx
	PT 2	x	x.x	xxx	x	x.x	xxx	x	x.x	xxx	x	x.x	xxx	x	x.x	xxx	x	x.x	xxx	x	x.x	xxx	x	x.x	xxx	x	x.x	xxx	x	x.x	xxx

TEAE= Treatment-emergent Adverse Event. n= Number of unique subjects that satisfies the row criteria. N=Number of subjects in the Safety population.

Denominators are the number of subjects in the Safety population.

If a subject has multiple occurrences of an adverse event, the subject is counted only once in the preferred term/system organ class category.

All adverse events were coded using the Medical Dictionary for Regulatory Activities (MedDRA) version 23.0.

^a There were X additional subjects with an Actual Baseline Ordinal Score of 4 that are included in the 'Any BOS' summaries.

Table with similar format:

Table 49: Treatment Emergent Adverse Events by System Organ Class, Preferred Term, and Baseline Steroid Use — Safety Population

Table 50: Treatment Emergent Adverse Events by System Organ Class, Preferred Term, and Baseline Use of Emerging Covid-19 Treatments — Safety Population

Table 51: Treatment Emergent Adverse Events by System Organ Class, Preferred Term, and Duration of Symptoms Prior to Enrollment — Safety Population

Table 52: Treatment Emergent Serious Adverse Events by System Organ Class, Preferred Term and Treatment Group — Safety Population

MedDRA Classification		Treatment A (N=X)			Treatment B (N=X)			Risk Difference	
System Organ Class	Preferred Term	n	%	Events	n	%	Events	Estimate	95% CI ^a
Any SOC	Any PT	x	x.x	xxx	x	x.x	xxx	x.x	x.x
SOC 1	Any PT	x	x.x	xxx	x	x.x	xxx	x.x	x.x
	PT 1	x	x.x	xxx	x	x.x	xxx	x.x	x.x
	PT 2	x	x.x	xxx	x	x.x	xxx	x.x	x.x
SOC 2	Any PT	x	x.x	xxx	x	x.x	xxx	x.x	x.x
	PT 1	x	x.x	xxx	x	x.x	xxx	x.x	x.x
	PT 2	x	x.x	xxx	x	x.x	xxx	x.x	x.x

TEAE= Treatment-emergent Adverse Event. n= Number of unique subjects that satisfies the row criteria. N=Number of subjects in the Safety population.

Denominators are the number of subjects in the Safety population.

If a subject has multiple occurrences of an adverse event, the subject is counted only once in the preferred term/system organ class category.

All adverse events were coded using the Medical Dictionary for Regulatory Activities (MedDRA) version 23.0.

^a 95% CI for risk differences calculated using the Miettinen-Nurminen method.

Table 53: Treatment Emergent Serious Adverse Events by System Organ Class, Preferred Term, and Baseline Ordinal Score — Safety Population

MedDRA Classification		Treatment A (N=X)											Treatment B (N=X)												
		Baseline Ordinal Score											Baseline Ordinal Score												
		5			6			7			Any BOS ^a			5			6			7			Any BOS ^a		
System Organ Class	Preferred Term	n	%	Events	n	%	Events	n	%	Events	n	%	Events	n	%	Events	n	%	Events	n	%	Events	n	%	Events
Any SOC	Any PT	x	x.x	xxx	x	x.x	xxx	x	x.x	xxx	x	x.x	xxx	x	x.x	xxx	x	x.x	xxx	x	x.x	xxx	x	x.x	xxx
SOC 1	Any PT	x	x.x	xxx	x	x.x	xxx	x	x.x	xxx	x	x.x	xxx	x	x.x	xxx	x	x.x	xxx	x	x.x	xxx	x	x.x	xxx
	PT 1	x	x.x	xxx	x	x.x	xxx	x	x.x	xxx	x	x.x	xxx	x	x.x	xxx	x	x.x	xxx	x	x.x	xxx	x	x.x	xxx
	PT 2	x	x.x	xxx	x	x.x	xxx	x	x.x	xxx	x	x.x	xxx	x	x.x	xxx	x	x.x	xxx	x	x.x	xxx	x	x.x	xxx
SOC 2	Any PT	x	x.x	xxx	x	x.x	xxx	x	x.x	xxx	x	x.x	xxx	x	x.x	xxx	x	x.x	xxx	x	x.x	xxx	x	x.x	xxx
	PT 1	x	x.x	xxx	x	x.x	xxx	x	x.x	xxx	x	x.x	xxx	x	x.x	xxx	x	x.x	xxx	x	x.x	xxx	x	x.x	xxx
	PT 2	x	x.x	xxx	x	x.x	xxx	x	x.x	xxx	x	x.x	xxx	x	x.x	xxx	x	x.x	xxx	x	x.x	xxx	x	x.x	xxx

TEAE= Treatment-emergent Adverse Event. n= Number of unique subjects that satisfies the row criteria. N=Number of subjects in the Safety population.

Denominators are the number of subjects in the Safety population.

If a subject has multiple occurrences of an adverse event, the subject is counted only once in the preferred term/system organ class category.

All adverse events were coded using the Medical Dictionary for Regulatory Activities (MedDRA) version 23.0.

^a There were X additional subjects with an Actual Baseline Ordinal Score of 4 that are included in the 'Any BOS' summaries.

Table 54: Mortality Rates — Safety Population

Analysis Type	Baseline Ordinal Score	Treatment Group	Number of Deaths		Mortality Rate (CI) ^e			Difference in Mortality Rates at the Specified Time Point ^d			HR ^e			P-value ^f
			n	%	Estimate	80% CI	95% CI	Estimate	80% CI	95% CI	Estimate	80% CI	95% CI	
Time to Death by Day 15														
Primary ^a	5	Treatment A (N=X)	X	x.x	x.x	x.x, x.x	x.xxx	x.x	x.x, x.x	x.x, x.x	x.x	x.x, x.x	x.x, x.x	0.xxx
		Treatment B (N=X)	X	x.x	x.xx	x.x, x.x	x.xxx							
	6	Treatment A (N=X)	X	x.x	x.x	x.x, x.x	x.xxx	x.x	x.x, x.x	x.x, x.x	x.x	x.x, x.x	x.x, x.x	0.xxx
		Treatment B (N=X)	X	x.x	x.xx	x.x, x.x	x.xxx							
	7	Treatment A (N=X)	X	x.x	x.x	x.x, x.x	x.xxx	x.x	x.x, x.x	x.x, x.x	x.x	x.x, x.x	x.x, x.x	0.xxx
		Treatment B (N=X)	X	x.x	x.xx	x.x, x.x	x.xxx							
Any BOS	Treatment A (N=X)	X	x.x	x.x	x.x, x.x	x.xxx	x.x	x.x, x.x	x.x, x.x	x.x	x.x, x.x	x.x, x.x	0.xxx	
	Treatment B (N=X)	X	x.x	x.xx	x.x, x.x	x.xxx								
Primary with Sensitivity Imputation ^b	5	Treatment A (N=X)	X	x.x	x.x	x.x, x.x	x.xxx	x.x	x.x, x.x	x.x, x.x	x.x	x.x, x.x	x.x, x.x	0.xxx
		Treatment B (N=X)	X	x.x	x.xx	x.x, x.x	x.xxx							
	6	Treatment A (N=X)	X	x.x	x.x	x.x, x.x	x.xxx	x.x	x.x, x.x	x.x, x.x	x.x	x.x, x.x	x.x, x.x	0.xxx
		Treatment B (N=X)	X	x.x	x.xx	x.x, x.x	x.xxx							
	7	Treatment A (N=X)	X	x.x	x.x	x.x, x.x	x.xxx	x.x	x.x, x.x	x.x, x.x	x.x	x.x, x.x	x.x, x.x	0.xxx
		Treatment B (N=X)	X	x.x	x.xx	x.x, x.x	x.xxx							
Any BOS	Treatment A (N=X)	X	x.x	x.x	x.x, x.x	x.xxx	x.x	x.x, x.x	x.x, x.x	x.x	x.x, x.x	x.x, x.x	0.xxx	
	Treatment B (N=X)	X	x.x	x.xx	x.x, x.x	x.xxx								
Time to Death by Day 29														
Primary ^a	5	Treatment A (N=X)	X	x.x	x.xx	x.x, x.x	x.xxx	x.x	x.x, x.x	x.x, x.x	x.x	x.x, x.x	x.x, x.x	0.xxx
		Treatment B (N=X)	X	x.x	x.xx	x.x, x.x	x.xxx							
	6	Treatment A (N=X)	X	x.x	x.x	x.x, x.x	x.xxx	x.x	x.x, x.x	x.x, x.x	x.x	x.x, x.x	x.x, x.x	0.xxx
		Treatment B (N=X)	X	x.x	x.xx	x.x, x.x	x.xxx							
7	Treatment A (N=X)	X	x.x	x.x	x.x, x.x	x.xxx	x.x	x.x, x.x	x.x, x.x	x.x	x.x, x.x	x.x, x.x	0.xxx	

Analysis Type	Baseline Ordinal Score	Treatment Group	Number of Deaths		Mortality Rate (CI) ^e			Difference in Mortality Rates at the Specified Time Point ^d			HR ^e			P-value ^f	
			n	%	Estimate	80% CI	95% CI	Estimate	80% CI	95% CI	Estimate	80% CI	95% CI		
	Any BOS	Treatment B (N=X)	X	x.x	x.xx	x.x, x.x	x.xxx								
		Treatment A (N=X)	X	x.x	x.x	x.x, x.x	x.xxx	x.x	x.x, x.x	x.x, x.x	x.x	x.x, x.x	x.x, x.x	0.xxx	
		Treatment B (N=X)	X	x.x	x.xx	x.x, x.x	x.xxx								
Primary with Sensitivity Imputation ^b	5	Treatment A (N=X)	X	x.x	x.xx	x.x, x.x	x.xxx	x.x	x.x, x.x	x.x, x.x	x.x	x.x, x.x	x.x, x.x	0.xxx	
		Treatment B (N=X)	X	x.x	x.xx	x.x, x.x	x.xxx								
	6	Treatment A (N=X)	X	x.x	x.x	x.x, x.x	x.xxx	x.x	x.x, x.x	x.x, x.x	x.x	x.x, x.x	x.x, x.x	0.xxx	
		Treatment B (N=X)	X	x.x	x.xx	x.x, x.x	x.xxx								
	7	Treatment A (N=X)	X	x.x	x.x	x.x, x.x	x.xxx	x.x	x.x, x.x	x.x, x.x	x.x	x.x, x.x	x.x, x.x	0.xxx	
		Treatment B (N=X)	X	x.x	x.xx	x.x, x.x	x.xxx								
	Any BOS	Treatment A (N=X)	X	x.x	x.x	x.x, x.x	x.xxx	x.x	x.x, x.x	x.x, x.x	x.x	x.x, x.x	x.x, x.x	0.xxx	
Treatment B (N=X)		X	x.x	x.xx	x.x, x.x	x.xxx									
Time to Death by Day 60															
Primary ^a	5	Treatment A (N=X)	X	x.x	x.xx	x.x, x.x	x.xxx	x.x	x.x, x.x	x.x, x.x	x.x	x.x, x.x	x.x, x.x	0.xxx	
		Treatment B (N=X)	X	x.x	x.xx	x.x, x.x	x.xxx								
	6	Treatment A (N=X)	X	x.x	x.x	x.x, x.x	x.xxx	x.x	x.x, x.x	x.x, x.x	x.x	x.x, x.x	x.x, x.x	0.xxx	
		Treatment B (N=X)	X	x.x	x.xx	x.x, x.x	x.xxx								
	7	Treatment A (N=X)	X	x.x	x.x	x.x, x.x	x.xxx	x.x	x.x, x.x	x.x, x.x	x.x	x.x, x.x	x.x, x.x	0.xxx	
		Treatment B (N=X)	X	x.x	x.xx	x.x, x.x	x.xxx								
	Any BOS	Treatment A (N=X)	X	x.x	x.x	x.x, x.x	x.xxx	x.x	x.x, x.x	x.x, x.x	x.x	x.x, x.x	x.x, x.x	0.xxx	
Treatment B (N=X)		X	x.x	x.xx	x.x, x.x	x.xxx									
Primary with Sensitivity Imputation ^b	5	Treatment A (N=X)	X	x.x	x.xx	x.x, x.x	x.xxx	x.x	x.x, x.x	x.x, x.x	x.x	x.x, x.x	x.x, x.x	0.xxx	
		Treatment B (N=X)	X	x.x	x.xx	x.x, x.x	x.xxx								
	6	Treatment A (N=X)	X	x.x	x.x	x.x, x.x	x.xxx	x.x	x.x, x.x	x.x, x.x	x.x	x.x, x.x	x.x, x.x	0.xxx	
		Treatment B (N=X)	X	x.x	x.xx	x.x, x.x	x.xxx								
	7	Treatment A (N=X)	X	x.x	x.x	x.x, x.x	x.xxx	x.x	x.x, x.x	x.x, x.x	x.x	x.x, x.x	x.x, x.x	0.xxx	

Analysis Type	Baseline Ordinal Score	Treatment Group	Number of Deaths		Mortality Rate (CI) ^c			Difference in Mortality Rates at the Specified Time Point ^d			HR ^e			P-value ^f
			n	%	Estimate	80% CI	95% CI	Estimate	80% CI	95% CI	Estimate	80% CI	95% CI	
		Treatment B (N=X)	X	x.x	x.xx	x.x, x.x	x.xxx							
	Any BOS	Treatment A (N=X)	X	x.x	x.x	x.x, x.x	x.xxx	x.x	x.x, x.x	x.x, x.x	x.x	x.x, x.x	x.x, x.x	0.xxx
		Treatment B (N=X)	X	x.x	x.xx	x.x, x.x	x.xxx							

CI= Confidence Intervals. N=Number of subjects in the Safety population. n= Number of unique subjects that satisfies the row criteria.

^a For the primary endpoint, all subjects whose last assessment was before the corresponding timepoint (Day 15 Visit, Day 29 Visit, Day 60 Visit) and were missing the event were censored at the date of last assessment.

^b Primary with Sensitivity Imputation: Same analysis as the initial model but subjects missing event and whose last assessment is before the corresponding timepoint (Day 15 Visit, Day 29 Visit, Day 60 Visit) are non-events for good discharges and censored at Day 15, Day 29, Day 60 respectively or at last assessment for subjects still hospitalized or discharged to LTAC, hospice care, or other hospital.

^c Mortality Rates are the Kaplan-Meier estimates.

^d Difference in mortality rates (80%, 95% CI) obtained from Kaplan Meier.

^e HR is the hazard ratio from the Cox Proportional Hazard Model adjusted for baseline ordinal score and baseline steroid use.

^f P-value is based on the Cox adjusted model.

Table 55: Time to Death through Day 15, 29, or 60 by Treatment Group: Restricted Mean Survival Time Analysis — Safety Population

Study Day	Treatment Group	Actual Baseline Ordinal Score	n	Restricted Mean Mortality Time (Days)		Difference	
				Estimate	95% CI	Estimate	95% CI
Day 15	Treatment A (N=X)	5	x	x.x	x.x, x.x	x.xx	x.xx, x.xx
	Treatment B (N=X)		x	x.x	x.x, x.x		
	Treatment A (N=X)	6	x	x.x	x.x, x.x	x.xx	x.xx, x.xx
	Treatment B (N=X)		x	x.x	x.x, x.x		
	Treatment A (N=X)	7	x	x.x	x.x, x.x	x.xx	x.xx, x.xx
	Treatment B (N=X)		x	x.x	x.x, x.x		
	Treatment A (N=X)	Any BOS	x	x.x	x.x, x.x	x.xx	x.xx, x.xx
	Treatment B (N=X)		x	x.x	x.x, x.x		

Repeat for Day 29 and Day 60

N= Number of subjects in the specified treatment group, actual baseline ordinal score, and analysis population.

n = Number of subjects who died by the specified study day.

Difference is the difference in the restricted mean mortality time between Active treatment and Placebo.

Table 56: Time to Death, SAE or Grade ≥ 3 TEAEs through Day 60 — Safety Population

Baseline Ordinal Score	Treatment Group	Number of Deaths or Grade >3 TEAEs		Event Rate (CI) ^a			Difference in Event Rates at the Specified Time Point ^b			HR ^c			P-value ^d
		n	%	Estimate	80% CI	95% CI	Estimate	80% CI	95% CI	Estimate	80% CI	95% CI	
5	Treatment A (N=X)	X	x.x	x.x	x.x, x.x	x.xxx	x.x	x.x, x.x	x.x, x.x	x.x	x.x, x.x	x.x, x.x	0.xxx
	Treatment B (N=X)	X	x.x	x.xx	x.x, x.x	x.xxx							
6	Treatment A (N=X)	X	x.x	x.x	x.x, x.x	x.xxx	x.x	x.x, x.x	x.x, x.x	x.x	x.x, x.x	x.x, x.x	0.xxx
	Treatment B (N=X)	X	x.x	x.xx	x.x, x.x	x.xxx							
7	Treatment A (N=X)	X	x.x	x.x	x.x, x.x	x.xxx	x.x	x.x, x.x	x.x, x.x	x.x	x.x, x.x	x.x, x.x	0.xxx
	Treatment B (N=X)	X	x.x	x.xx	x.x, x.x	x.xxx							
Any BOS	Treatment A (N=X)	X	x.x	x.x	x.x, x.x	x.xxx	x.x	x.x, x.x	x.x, x.x	x.x	x.x, x.x	x.x, x.x	0.xxx
	Treatment B (N=X)	X	x.x	x.xx	x.x, x.x	x.xxx							

CI= Confidence Intervals. N=Number of subjects in the Safety population. n= Number of unique subjects that satisfies the row criteria.

^a Event rates are the Kaplan-Meier estimates.

^b Difference in event rates (80%, 95% CI) obtained from Kaplan Meier.

^c HR is the hazard ratio from the Cox Proportional Hazard Model adjusted for baseline ordinal score and baseline steroid use.

^d P-value is based on the Cox adjusted model.

